Specific Aim 1: To test the hypothesis that provision of serial body fat accrual reports during hospitalization will enable personalized dietary interventions and reduce adiposity at 3 months of age in very preterm infants. We chose %BF at 3 months of age as the primary outcome of the trial because at this age: 1) body fat accrual can be measured with non-invasive methods¹⁰; 2) loss to follow-up rates are low⁹; 3) physical activity and other risk factors for obesity are less likely⁷; and 4) correlation with body fat accrual at preschool age is strong⁹. We selected very preterm infants as the ideal population to study the risk of obesity in preterm infants because they: 1) experience a high risk for adverse health outcomes^{3,5}; 2) usually do not require supplemental oxygen after postnatal day 7; and 3) receive strictly controlled diets for more than 30 days from birth to hospital discharge. With our improved understanding of the interaction between infant weight, body fat accrual, and dietary interventions, we plan to examine whether the provision of body fat accrual reports to clinicians and parents will impact infant weight gain and body fat accrual¹¹.

Specific Aim 2: To test the hypothesis that serial assessment of infant body composition attenuates health disparities in body fat accrual at 3 months of age by slowing weight gain following hospital discharge. The rationale for this aim is: 1) rapid weight gain during early infancy is highly prevalent among racial/ethnic minorities^{12,13}; and 2) adjustment for rapid weight gain attenuates disparities in childhood obesity between racial/ethnic minorities and white infants^{7,12}. We hypothesize that our intervention focused on personalized dietary interventions based on changes in infant body composition will reduce rapid weight gain and attenuate health disparities in body fat accrual.

RESEARCH STRATEGY

SIGNIFICANCE

Rapid weight gain increases the risk of metabolic reprogramming in preterm infants. For many years, the high prevalence of postnatal growth failure (weight below the 10th percentile for expected intrauterine growth) in the preterm population made weight the most important outcome of growth among preterm infants. Similarly, the association between rapid weight gain and improved neurodevelopment led clinicians to assume that slow weight gain was “inadequate growth” and that high-calorie diets to promote rapid weight gain were needed.

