Available clinical evidence no longer supports these assumptions. Current dietary interventions have not appreciably reduced postnatal growth failure. Postnatal growth failure remains prevalent and occurs in approximately 60%¹⁴⁻¹⁶ of the nearly 80,000 infants born preterm at 32 weeks of gestation or less every year in the United States². Similarly, the benefits of rapid weight gain on neurodevelopment of preterm infants have not been consistently demonstrated. While 19 observational studies of low to moderate quality have associated rapid weight gain with improved neurodevelopmental outcomes¹⁷, 3 randomized trials of hospital-based nutritional interventions that reversed postnatal growth failure through rapid weight gain did not show benefits in neurodevelopment¹⁸⁻²⁰. These inconsistencies between results from randomized trials and results from low to moderate quality observational studies suggest the presence of unmeasured confounding factors that affect both growth and cognition¹⁷ and demand caution with the assumption that promoting brain development through rapid weight gain outweighs the risk of potential long-term metabolic dysfunction.

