Rapid weight gain also known as catch-up growth could trigger changes in metabolic reprogramming. Results from interventional and observational studies indicate that high-calorie diets before and after hospital discharge to promote catch-up growth and prevent postnatal growth failure among preterm infants²¹ may result in hypertension, insulin resistance²², and disproportionate increase of body fat^{17,23}, particularly when carbohydrates and fat are the primary source of energy. This clinical evidence of metabolic dysfunction resulting from rapid weight gain has been demonstrated in humans and animal models. Clinical studies consistently show that growth-restricted preterm infants are more likely to experience catch-up growth^{15,24} and corroborate conclusions from animal experiments that reveal an increased susceptibility to early metabolic reprogramming of adverse health outcomes in developing infants exposed to high-calorie diets^{17,25,26}. In rats and mice with growth restriction as a result of poor maternal diet, rapid growth due to high-calorie diets increases susceptibility to obesity and reduces longevity^{27,28}. The mechanisms of early metabolic reprogramming include permanent changes in organ structure due to suboptimal nutrition, epigenetic modifications that lead to changes in gene expression, and permanent effects on regulation of cellular aging²⁵.

Assessment of infant body composition offers important advantages over BMI as outcome of growth. BMI and infant body composition are outcomes of growth associated with long-term health. BMI is a widely accepted anthropometric index that is used to define obesity, but in early infancy, BMI has poor predictive accuracy for obesity and poor correlation with body fat accrual. In term infants, BMI only explains up to 43% of the variation in fat mass (FM)^{29,30}. Furthermore, reduction of infant BMI to prevent obesity in adulthood is not currently recommended because high infant BMI values are associated with greater lean mass³¹. Body fat accrual during early infancy is a marker of fetal adaption and metabolic reprogramming that has a significant association with obesity and other adverse health outcomes³². Rapid weight gain is associated with higher risk of %BF, abnormal fat distribution, and overweight at school age^{8,33}.

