Setting: The neonatal unit at UAB is one of the largest neonatal academic centers in the United States. We have admitted more than 200 very preterm infants over the past 2 years. This large numbers of very preterm infants admitted makes our unit the ideal environment to conduct comparative effectiveness trials.

Participants: Very preterm infants with gestational ages between 28 and 32 weeks of gestation at the time of admission to our neonatal unit will be eligible for this trial. Gastrointestinal or neurologic malformations, and terminal illness requiring limited or withheld support will be exclusion criteria.

[figure not shown]
Randomization, allocation concealment, and masking: After receiving approval by the Institutional Review Board (IRB) at UAB to conduct this trial, research nurses and investigators will obtain written parental consent before randomization. We will randomize study participants using computer generated random-block sequences and numbered, opaque, sealed envelopes that will be opened in sequential order. Twin infants will be randomized individually. The intervention will not be masked.

Intervention: Infants randomly assigned to the intervention group will have the information about infant body composition known to the clinicians caring for them (including reference data). The use of this patient-specific information about nutritional status will assist clinicians to optimize nutrition using feeding guidelines that will be provided. Infants randomly assigned to the control group will also undergo serial measurements of body composition, but this information will not be available to the clinicians.

Primary and secondary outcomes: The primary outcome will be %BF estimated by air displacement plethysmography at 3 months of age. Secondary outcomes will include %BF and fat-free mass (FFM) at 36 weeks of postmenstrual age (PMA) or hospital discharge (whichever occurs first), postnatal growth restriction (below 10th percentile) at 36 weeks PMA or discharge, weight gain (g/kg/d) from birth to the end of the intervention, anthropometric measures at time of hospital discharge (weight, head circumference, and length), weight gain (g/kg/d) from hospital discharge to 3 months of age, anthropometric measures at 3 months of age (weight, head circumference, and length), and blood pressure values at 3 months of age.

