Protections against Risk. Our team will make every effort to protect all participants' confidential and private information in order to minimize possible study-associated risks. All findings related to any research will be available and provided to study participants in accordance with standard practices. We will also inform all participants that their participation is voluntary, and we will utilize study identification codes in place of personal identifiers on study materials. We will also employ storage and encryption techniques in compliance with UAB Data Security standards to safeguard all electronic data, as well as protections outlined in Subpart C of title 45, part 4 Code of Federal Regulations. All study personnel are required to renew Human Subjects training biannually. No data will be accepted from or distributed to the principal investigator or study staff if regulatory training is not current.

Any provider or caregiver involved in the trial will be able to write to the study coordinator to draw attention to any concern they may have about the possibility of harm arising from the intervention under investigation.

Potential Benefits of the Proposed Research to Human Subjects and Others

Potential benefits of this study are to provide stronger evidence for the safety and efficacy of monitoring body fat accrual as a way of optimizing caloric intake, growth, and fat-free mass in preterm infants. Better quantitative and qualitative outcomes of growth may also be associated with improved long-term neurodevelopmental outcomes.

The potential benefits of this research may include reduction of postnatal growth restriction, reduction in infant morbidity mediated through improved neonatal nutrition, and better growth at time of discharge. Reductions of postnatal growth restriction and improved nutritional parameters could improve long-term neurodevelopmental outcomes of infants. There will be benefit to the medical community in providing additional information on infant body composition in preterm infants.

Importance of the Knowledge to be Gained

As the risk to individual participants is small and potential benefits are significant, the risk/benefit ratio is favorable.

ClinicalTrials.gov Requirements

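### The postnatal growth restriction outcome is a cut-off at one time point that takes no account of size at birth; add a weight z-score analysis anchored at birth (minor)

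*Combined protocol and SAP*

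**What the plan says.** The secondary outcomes (Study design, Primary and secondary outcomes) include "postnatal growth restriction (below 10th percentile) at 36 weeks PMA or discharge". That sentence names no growth chart, no body measure and no condition on percentile at birth. The Significance section supplies a measure and a reference for what appears to be the same construct: "postnatal growth failure (weight below the 10th percentile for expected intrauterine growth". It too sets no birth condition.

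Eligibility rests on gestation alone: "Very preterm infants with gestational ages between 28 and 32 weeks of gestation at the time of admission to our neonatal unit will be eligible". Small size at birth is not an exclusion: "Gastrointestinal or neurologic malformations, and terminal illness requiring limited or withheld support will be exclusion criteria". The Statistical Analysis Plan paragraph foresees adjustment for demographic and nutritional characteristics, with a similar approach for secondary outcomes, but names no covariates, so birth size is not a stated one.

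Other growth outcomes are listed. They are "weight gain (g/kg/d) from birth to the end of the intervention", weight gain in g/kg/d from discharge to 3 months, and weight, length and head circumference at discharge and at 3 months. The list does not say that any of these will be expressed relative to expected growth.

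Under Potential Benefits the protocol states: "The potential benefits of this research may include reduction of postnatal growth restriction".

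**The concern.** The outcome's name refers to growth after birth, but its definition also captures size before birth. An infant born below the 10th percentile who remains there is an event, although the restriction did not begin after birth. An infant who drops from the 90th to the 11th percentile is not an event, although that is a marked loss of growth.

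This matters because the intervention aims at lower body fat, and Aim 2 expects slower weight gain after discharge. The Rationale for Aim 1 states the goal as adequate nutrition that prevents growth failure without adding health risk. A reader of the results will want to know whether growth relative to expectation was preserved. Among the listed outcomes, this is the only one defined against a percentile, and part of what it reports was settled before randomization.

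**Working it through.** **Plan's own figures.** The documents give no rate, effect or power for this outcome. The only sample-size figure concerns the primary outcome, and it reproduces: n per arm = 2(1.96+0.84)²(3.6)²/3² = 22.6, rounded up to 23, or 46 in total, raised to 50. It does not bear on this point beyond fixing 25 per arm.

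**Inputs.**
- 25 per arm (Sample Size and Power Estimates).
- Overall event rate 60%, from the Significance section: "Postnatal growth failure remains prevalent and occurs in approximately 60" percent of infants born at 32 weeks or less. This is a US background rate, not a planning assumption for the control arm.
- Share below the 10th percentile at birth, s: not in the documents; assumed 10-20%.
- Share of those still below at 36 weeks PMA or discharge, q: not in the documents; 100%, 90% and 75% shown, and 50-100% for the event counts.

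**1. Events from infants small at birth.** Expected events per arm are 25 × 0.60 = 15. Infants small at birth supply 25·s·q. For s = 10% that is about 1.2 to 2.5 events (8-17%) as q runs from 50% to 100%. For s = 20% it is 2.5 to 5.0 events (17-33%).

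**2. Chance imbalance.** The SD of the between-arm difference in the share small at birth is √(2s(1−s)/25), which is 8.5 points for s = 10% and 11.3 points for s = 20%. To carry this into the outcome, multiply by the gap in event rate between infants small at birth (q) and the others, (0.60 − s·q)/(1 − s).

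| s | q | Rate in others | Gap | SD in outcome difference |
|---|---|---|---|---|
| 10% | 100% | 55.6% | 44.4 points | 8.5 × 0.444 = 3.8 points |
| 20% | 100% | 50.0% | 50.0 points | 11.3 × 0.500 = 5.7 points |
| 10% | 90% | 56.7% | 33.3 points | 2.8 points |
| 20% | 90% | 52.5% | 37.5 points | 4.2 points |
| 10% | 75% | 58.3% | 16.7 points | 1.4 points |
| 20% | 75% | 56.3% | 18.8 points | 2.1 points |

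These SDs are a component of the total, not an addition to it. The total SD of the difference is √(2 × 0.6 × 0.4/25) = 13.9 points, a 95% half-width of 27 points. With q = 100%, size at birth accounts for s(1−s)·gap²/0.24 of the outcome variance: 0.09 × 0.198/0.24 = 7% and 0.16 × 0.25/0.24 = 17%.

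**3. Dilution.** A 20-point effect (assumed) confined to infants not small at birth becomes 20 × (1 − s) = 18 points (s = 10%) or 16 points (s = 20%) across all infants. Power is then 28% for all infants against 29-31% for new cases only at s = 10%, and 22% against 25-29% at s = 20%. Counting only new cases therefore gains about 1 to 7 points.

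**4. Cut-off against z-score.** Assume attained weight z has SD 1.0 and the intervention lowers it by 0.5. A 60% rate corresponds to a standard normal value of 0.253; adding 0.5 gives 0.753, a rate of 77%. By the arcsine approximation, h = 2(arcsin√0.774 − arcsin√0.60) = 0.38, and power = Φ(0.38 × √12.5 − 1.96) = 27%. A two-sided t-test of the same 0.5 shift on change in z-score, 25 per arm, has power of 41%, 70% and 93% for an SD of change of 1.0, 0.7 and 0.5. None of these SDs is in the documents. The 41% equals what attained z with SD 1.0 would give, so at that end the gain comes only from not dichotomizing.

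**The case against.** The strongest reply is that this is one unpowered secondary outcome in a 50-infant pilot, that its cut-off matches the protocol's own definition of growth failure and the 60% rate it cites, and that randomization balances birth size in expectation. All of that stands, and it limits the point to a minor one. Several stronger readings are tempting but not supported.

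- A reader might infer that infants small at birth are events that neither arm can influence. Their restriction began before birth, but its persistence can change with feeding, and the Significance section says that "growth-restricted preterm infants are more likely to experience catch-up growth".
- A reader might take the 8.5-11.3 point SD in the share small at birth (95% range about ±17 to ±22 points) as the disturbance in the outcome. It is not: the other infants also have events, so the component is 3.8-5.7 points at most under these inputs.
- A reader might treat this outcome as the trial's measure of growth harm. No section gives it a safety role; the protocol lists its reduction as a possible benefit.
- A reader might infer that growth after discharge is not covered. Weight gain to 3 months and the 3-month measurements cover it.

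It can also be said that "weight gain (g/kg/d) from birth to the end of the intervention" is already continuous and anchored at birth, and would register a fall from the 90th to the 11th percentile. That is partly right. But g/kg/d is not referenced to expected growth for sex and gestation, so it does not show by itself whether an infant kept or lost position. The planned adjusted analysis offers a route to handle birth size, but birth size is not named in it.

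**Conclusion.** The point holds at minor severity. As defined, the outcome mixes prenatal size with postnatal change, and no exclusion, baseline condition or named covariate separates them. The consequence is dilution and chance imbalance, not systematic bias. With 10-20% small at birth and all remaining below the 10th percentile, imbalance at entry contributes an SD of about 4-6 points out of a total of 13.9; with catch-up it contributes less. The true size cannot be fixed from the documents, because neither the share small at birth nor its persistence is given.

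The larger practical loss is precision: 27% power with the cut-off against 41-93% with change in z-score for a 0.5 z fall, under assumed SDs. Restricting the count to new cases would not recover this. The primary outcome and the sample size are not affected.

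**What to change.** Add, as the main growth-restriction analysis, the sex- and gestational-age-specific weight z-score at 36 weeks PMA or discharge, analysed as change from birth or adjusted for birth z-score. Name the growth chart. Express the already planned 3-month weight, length and head circumference the same way, stating the reference and the age basis used at that visit.

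Keep the 10th-percentile outcome as supportive. State that it refers to weight, if that is the intent, and report it in each arm separately for infants at or above and below the 10th percentile at birth.

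The cost is slightly more analysis work and a few lines of text. Birth weight is already needed for weight gain from birth. Length and head circumference at birth are not named in the outcome list and are assumed to be available from the medical record. No visits or patients are added, and the primary outcome and N=50 stay as they are.

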Study specimens. Because several experiments suggest that changes in gut microbiota can influence obesity⁴⁸, we will obtain written informed consent from the parent(s) to collect 2 stool samples, 1 stool sample before hospital discharge and 1 stool sample at the 3-month follow-up visit for possible use in future studies. Similarly, consent from the parent(s) will be obtained to collect a serum sample and measure biomarkers of anabolism and growth prior to hospital discharge.

Statistical Analysis Plan. This trial will record core data on nutrition as recommended by consensus groups⁴⁹. For analysis of the primary outcome, an unadjusted T-test comparison of the mean %BF between control and intervention groups will be performed assuming a normal distribution of this variable⁵⁰. In consideration of relevant biological variables, a pre-specified adjusted analysis for demographic and nutritional characteristics will be conducted to improve precision in treatment comparisons and remove variability associated with these covariates^{51,52}. A similar approach will be used for secondary outcomes. Descriptive data will be expressed as the mean (SD) or number (percentage) of observations. The primary statistical analyses will be performed on an intention-to-treat basis⁴⁹ with SAS software.

Sample Size and Power Estimates. At our institution, the mean and SD of %BF in preterm infants at time of discharge is 15 and 3.6, respectively (unpublished data). Therefore, to detect a 3-point difference in %BF between groups with SD of 3.6, 0.05 level of significance, and 80% power for a T-test that compares means from two independent samples, a sample size of 46 patients will be necessary in this superiority trial. Anticipating that approximately 10% of study participants will be lost to follow-up for assessment of the primary outcome at 3 months of age, 2 patients will be added to each group and the sample size will be increased to 50. We will include a total of 25 patients in each group (n=50).

Potential Problems

Enrollment rates: An average of 7 study participants per month were enrolled in a recently completed trial that assessed body composition of very preterm infants at our institution (unpublished data). To define a timeline for patient enrollment in this trial, we assumed that 50% of parents will refuse participation.

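### The only size-for-age outcome at 36 weeks PMA or discharge is a yes/no cut at the 10th percentile; a weight z-score from the same data would be more powerful at almost no cost

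*Combined protocol and SAP*

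**What the plan says.** The outcome list (APPROACH, Study design, Primary and secondary outcomes) includes "postnatal growth restriction (below 10th percentile) at 36 weeks PMA or discharge". It does not name the measure being cut. The SIGNIFICANCE section describes "postnatal growth failure (weight below the 10th percentile for expected intrauterine growth"), so weight against an intrauterine reference is the natural reading. The text names no reference chart.

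The same list has continuous growth outcomes: "anthropometric measures at time of hospital discharge (weight, head circumference, and length"), "weight gain (g/kg/d) from birth to the end of the intervention", and post-discharge equivalents up to 3 months. It gives no z-score and no percentile on its full scale.

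For analysis, the Statistical Analysis Plan sets an unadjusted t-test followed by an adjusted analysis for the primary outcome, then says "A similar approach will be used for secondary outcomes". It names no test for a binary outcome. The sample size paragraph ends: "We will include a total of 25 patients in each group (n=50").

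Two further passages bear on this outcome. SIGNIFICANCE gives a background frequency: "Postnatal growth failure remains prevalent and occurs in approximately 60" per cent, for infants born at 32 weeks or less. The section on potential benefits says: "The potential benefits of this research may include reduction of postnatal growth restriction".

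**The concern.** A cut at the 10th percentile treats an infant who ends at the 9th percentile and one who ends at the 2nd as the same result, and likewise infants at the 12th and the 60th. Differences between arms count only when they carry infants across the line. With 25 infants per arm, the lost information matters.

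The outcome has a real role. The intervention is meant to reduce body fat and slow weight gain, and less growth restriction is named as a possible benefit. Attained size for age is therefore a natural place to look for help or harm to growth. A weak comparison makes a non-significant result more likely when the arms truly differ, and such a result is easily read as showing no effect on growth. The documents cite no guideline or regulator that requires the yes/no form.

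**Working it through.** **The plan's own figure.** For 3 points, SD 3.6, two-sided 0.05 and 80% power, the normal formula gives n per arm = 2 × (1.960 + 0.842)² × 3.6² / 3² = 2 × 7.849 × 1.44 = 22.6, so 23 per arm and 46 in all. This matches the stated 46, later raised to 50. It concerns %BF at 3 months. The documents state no power, effect size or planning rate for growth restriction.

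**Inputs for the comparison.**
- 25 infants per arm: sample size paragraph.
- Two-sided 0.05: the level is stated; the sidedness is inferred because it reproduces the 46.
- Control rate 60%: the background figure in SIGNIFICANCE, used here as an assumption.
- Shift d in SD units of the weight z-score: assumed. The values are 0.3, 0.5 and 0.83, the last being 3/3.6, borrowed from the primary outcome for scale only.
- Normal z-score with equal SD in both arms, infants independent: assumed. Twins are randomised individually, and this is ignored.

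**Formulas.** z-score: t-test power from the noncentral t with 48 degrees of freedom and noncentrality d × √(25/2), which is 1.06, 1.77 and 2.95 for the three shifts. Yes/no outcome: the rate in the other arm is Φ(Φ⁻¹(0.60) ± d), with Φ⁻¹(0.60) = 0.253. The power of the Pearson chi-square and Fisher tests is then summed exactly over all pairs of binomial counts.

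| Shift | Rate, control to intervention | t-test on z-score | Chi-square (loss) | Fisher (loss) |
|---|---|---|---|---|
| 0.3 SD, smaller infants | 60% to 71% | 18% | 14% (4) | 8% (10) |
| 0.3 SD, larger infants | 60% to 48% | 18% | 16% (2) | 10% (8) |
| 0.5 SD, smaller | 60% to 77% | 41% | 28% (13) | 17% (24) |
| 0.5 SD, larger | 60% to 40% | 41% | 33% (8) | 23% (18) |
| 0.83 SD, smaller | 60% to 86% | 82% | 58% (25) | 43% (40) |
| 0.83 SD, larger | 60% to 28% | 82% | 68% (15) | 56% (26) |

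Losses are in percentage points, taken before rounding.

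**Sensitivity.** With a control rate of 30% or 45% and a 0.83 SD shift, chi-square power is 51% to 68%, a loss of 14 to 31 points. With 23 per arm at the 60% rate, the loss against chi-square for 0.5 to 0.83 SD is 10 to 26 points. From 60%, the chi-square test reaches 81% power when the intervention arm is at 92%.

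**What the z-score can and cannot show.** With 25 per arm, the 95% confidence interval for a mean difference has a half-width of about 2.01 × √(2/25) = 0.57 SD.

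**The case against.** The strongest reply is that continuous growth information is largely kept. Discharge weight, length and head circumference and in-hospital weight gain are all separate outcomes. For an infant discharged by 36 weeks PMA, discharge weight is essentially the measurement behind the cut. Variation in PMA at discharge adds noise to both arms and does not by itself bias a randomised comparison. This mostly stands. A reader might infer that weight in hospital is examined only as yes or no; the outcome list contradicts that. What remains is narrower. Raw discharge weight mixes growth with length of stay, g/kg/d is a rate and not attained size, and the adjusted analysis does not itemise its covariates, so adjustment for PMA is not assured.

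The second reply is that the inputs are borrowed. The 0.83 SD belongs to %BF at 3 months. The 60% covers infants born at 32 weeks or less, with no lower limit, whereas the trial enrols from 28 weeks. No binary test is named. This also stands, so the loss is a range under assumptions and not a property of the trial.

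The third reply is that changing scale does not prevent a misreading. At 0.5 SD the z-score test would still miss the shift more often than not. This is correct: the interval, more than the scale, guards against reading a null result as no growth cost. The protocol itself warns, under Generalizability, that its small sample limits precision.

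Finally, this is one secondary outcome of a pilot, with no power claim or safety margin attached, and the cut allows comparison with published rates. That supports keeping the percentage, but not making it the only standardised analysis.

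**Conclusion.** The point holds as a cheap improvement to a secondary outcome. The one reference-standardised size outcome is dichotomised, and the z-score behind it had more power in every scenario computed. At an assumed 60% control rate with 25 per arm, the cut costs about 8 to 25 points against chi-square for shifts of 0.5 to 0.83 SD, and 18 to 40 against Fisher. At 0.3 SD the cost against chi-square is only about 2 to 4 points, because neither analysis has much power there. These figures rest on the assumed shift, control rate, normality, equal SD and independence of infants.

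Two stronger readings should be avoided. One is that the sample size or a stated power is wrong: the 46 reproduces, and nothing is claimed for growth restriction. The other is that a z-score would settle whether the intervention affects growth: at 41% power for 0.5 SD and a half-width of about 0.57 SD, it would not.

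**What to change.** In the outcome list, define this outcome as the weight-for-PMA-and-sex z-score at 36 weeks PMA or discharge, whichever occurs first, on a named intrauterine reference. Analyse it as a mean difference with a 95% confidence interval under the approach already set for secondary outcomes, which suits a continuous variable. Keep the number and percentage below the 10th percentile on the same reference as a companion result, with a confidence interval for the risk difference. State that a non-significant result will be interpreted from the interval and not as evidence of no growth cost.

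The cost is a few sentences. Weight, PMA and sex are already needed to classify the 10th percentile, so no new measurement and no extra infants are required. One reference chart must be chosen, which a 10th-percentile classification needs in any case. A z-score difference is also less familiar to clinicians than a percentage, which is why the percentage stays.
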